Title: Low-Dose versus High-Dose Oxytocin Dosing for Induction and Augmentation of Labor:
A Randomized Control Trial

Principle Investigator: [name]

Faculty Supervisor: [name]

Funding: Departmental

IRB number: 22-0240

1. Introduction and Purpose:

There is a nationwide trend of increasing elective induction of labor (IOL). The national rate of induction of labor in 2020 was 31.4%(1) vs. 27.1% in 2013(2). This trend can only be expected to increase further with the implementation of elective 39-week gestation IOL for maternal and neonatal benefits(3) and maternal medical comorbidities. Elective induction of labor is known to take longer than spontaneous labor(3, 4). Additionally, with any labor (induced or spontaneous), the possibility of failure to progress exists. Currently, the leading cause of primary cesarean delivery (CD) is labor dystocia(5, 6), and cesarean deliveries are associated with worse maternal and neonatal outcomes(7). Therefore, it is vital to research safe but effective methods for induction and augmentation of labor. The optimal regimen would result in the highest percentage of vaginal deliveries within the shortest period, with the lowest maternal and neonatal adverse outcomes. Low-dose and high-dose oxytocin protocols for labor have been endorsed by the American College of Obstetricians and Gynecologists (ACOG)(8). Currently, both regimens are considered standard of care at our institution and are being used during induction and augmentation of labor (AOL). Our hypothesis is that high-dose oxytocin results in a shorter time to vaginal delivery compared to low-dose regimen. The goal of this study is to examine the time from initiation of oxytocin titration to delivery in nulliparous individuals undergoing either induction or augmentation of labor.

2. Background:

ACOG has endorsed low-dose and high-dose oxytocin protocols for labor (8). However, no consensus has been reached regarding optimal oxytocin dosing. Previous research has suggested that high-dose oxytocin protocols may decrease total labor duration without an increase in cesarean delivery rates (5, 9-11). The leading concern regarding high-dose protocols revolves around uterine tachysystole, its hypothetical effect on fetal well-being, and a possible increase in cesarean delivery rates for fetal distress.

Different oxytocin dosing protocols have been studied in induction and AOL. One recent study studying the effect of oxytocin dosing in the augmentation of labor at one institution in the United States showed a reduction of primary cesarean delivery with high-dose oxytocin without an increase in obstetric or neonatal morbidity(9). A similar Swedish study showed no significant change in cesarean delivery rates(10). In that study and a systematic review of oxytocin dosing protocols for AOL, while high-dose oxytocin did increase the incidence of uterine tachysystole, this did not translate to an increase in CD for fetal distress (5, 10). Similar outcomes were seen for the induction of labor. An Australian study showed no change in cesarean or operative vaginal delivery (OVD) with different oxytocin dosing(11). A Cochrane review, including 9 studies, showed no significant difference in the mode of delivery, severe maternal morbidity, and

uterine hyperstimulation resulting in fetal distress with different oxytocin dosing(12). A significant limitation of these studies, however, includes patient homogeneity. While there is more research regarding optimal dosing for AOL, such information is sparse for labor induction.

Currently, at our institution, there is a similar lack of data regarding optimal oxytocin dosing. A change to our standard of care for oxytocin administration for augmentation of labor was introduced at the beginning of 2022, based on data from a randomized control trial performed at another institution (9). Under this new protocol, patients who meet criteria are eligible for either low-dose or high-dose oxytocin. The decision on which protocol to use is based mostly on provider preference while both dosing protocols are considered standard of care. While the safety of high-dose oxytocin has been previously established (5, 9-12), familiarity with low-dose oxytocin leads most providers to choose the low-dose protocol even when patients qualify for high-dose oxytocin. Thus, this study is crucial to further demonstrate the efficacy of high-dose oxytocin in our patient population and provide evidence to guide providers' decision-making regarding oxytocin dosing.

3. Concise Summary of Project:

This will be a randomized control clinical trial. The study period will be between January 1st, 2023 and January 1st, 2025. The number of subjects studied will be 170 patients at UTMB. The target population for our study is women who present for IOL or AOL at term. If the obstetric team decides that oxytocin infusion is required for labor in a subject meeting the inclusion criteria for the study, the subject will be consented and randomized to either the High Pit group (high-dose oxytocin) or the Low Pit group (low-dose oxytocin). Every subject who is enrolled in the study will meet the inclusion and exclusion criteria for both low- and high-dose oxytocin protocols (refer to inclusion criteria for this protocol). A subject meeting criterion for high-dose oxytocin will not preclude her from receiving low-dose oxytocin, and vice versa. Both study groups will otherwise receive the standardized labor management as currently performed at UTMB. The subjects will receive the same care and expertise as any other patient treated in our unit. Decisions regarding intrapartum management outside of oxytocin dosages will be left to the discretion of the obstetric provider. The trial will be considered completed whenever the target sample size number is reached. If we need more than the anticipated subjects to be enrolled, the trial will be paused, and a protocol addendum will be submitted to the IRB.

The **Low Pit group** will receive an infusion to start at 2 milli-units/min and will be increased by 2 milli-units/min every 20 minutes. The maximum rate of infusion is 40 milli-units/min.

The **High Pit group** will receive an infusion to start at 6 milli-units/min and will be increased by 6 milli-units/min every 20 minutes. Maximum rate of infusion is 40 milli-units/min.

Subjects in both group assignments will otherwise receive standard intrapartum care. The total participation time in the study will be considered terminated following delivery. Details for the procedure for the control group and study group can be found below. Both groups will be receiving the standard of care for IOL and AOL as both dosing protocols are currently being used at our institution.

4. Study Procedures:

Visit #1

4.1 Recruitment, Screening, and Consenting:

Under the direction of the PI, trained research staff will be available on the labor and delivery unit to screen and consent eligible subjects according to study protocol. We will review records of all nulliparous pregnant patients admitted to L&D for IOL or AOL at term who have had a decision made by their managing obstetric team to start an oxytocin infusion for induction or augmentation of labor who meet the inclusion and exclusion criteria below. Subjects will be enrolled before oxytocin infusion is ordered but after a decision has been made that oxytocin infusion is necessary. Subjects will be recruited, enrolled, and consented in a private room on labor and delivery or triage units to respect the privacy of potential subjects.

Subjects will be given all the time needed to fully read and understand the consent forms. All efforts will be made by the research staff to answer all questions the subject has and to ascertain that the subjects have the right to refuse to participate in the study. Subjects will be reassured that participation in the study is voluntary and will not interfere with the diagnosis or treatment of her condition. Non-English-speaking subjects are anticipated to be part of the study population and informed consent will be provided in their primary language. For non-English-speaking subjects, a certified interpreter will review the consent with them. Additionally, the consent form will be translated and provided in Spanish after initial IRB approval. A screening log will be used to track all subjects approached for the study using the Oncore system.

4.2 Operationalization

Randomization:

A confidential computer-generated simple randomization scheme (using STATA 17, Dallas, TX) will be prepared. A randomization log with group assignment, subject name, and medical record number will be used to track the randomization process. Subjects will be randomized in a ratio of 1:1 for low-dose or high-dose oxytocin infusion using the prepared computer-generated randomization scheme. Due to the nature of this intervention, blinding will not be possible. The subject will be included in the analysis by intent-to-treat once the randomization assignment has been made. The trial will be considered completed whenever the final enrollment number is reached. If we need more than the anticipated 170 patients to be enrolled, the trial will be paused, and a protocol addendum will be submitted to the IRB.

Labor and Delivery Unit and Staff:

Several training sessions will occur to notify all staff of the trial and the protocol. The training sessions will include a copy of the protocol, which will also be included in a follow-up email communication. All operations will be reviewed with all staff. The PI will be available for questions. An Epic order will be placed by the provider specifying oxytocin dosing according to the randomization assignment using a prepopulated “Order Set”.

4.3 Administration of Oxytocin Infusion

The Low Pit group will receive a controlled infusion pump at a proximal port on the peripheral IV line. The infusion will start at 2 milli-units/min and will be increased by 2 milli-units/min every 20 minutes. Maximum rate of infusion is 40 milli-units/min. Oxytocin infusion rate is adjusted to maintain adequate uterine contractions.

The High Pit group will receive a controlled infusion pump at a proximal port on the peripheral IV line. The infusion will start at 6 milli-units/min and will be increased by 6 milli-units/min every 20 minutes. Maximum rate of infusion is 40 milli-units/min. Oxytocin infusion rate is adjusted to maintain adequate uterine contractions.

Additional information regarding management of the oxytocin infusion in both groups:

- Initiation of the oxytocin infusion will be performed by the managing nurse as is standard of care at UTMB.
- The oxytocin infusion may be continued at a lower rate or discontinued at the discretion of the managing obstetric team for the usual obstetric reasons (e.g., changes in fetal heart tracing indicative of fetal distress, uterine tachysystole, suspected oxytocin adverse effects, and patient request)
- Oxytocin dosing may be decreased for uterine tachysystole (defined as >5 contractions/10 min, averaged over 30 minutes(13)) according to our current standard of care guidelines below
 - o Uterine tachysystole with category I FHTs
 - Reposition patient
 - Decrease oxytocin to $\frac{1}{2}$ the current dose
 - If tachysystole persists 15 minutes after the interventions, discontinue oxytocin until contractions return to <5 contractions/10 minutes
 - o Uterine tachysystole with category II or III FHTs
 - Decrease (category II) or discontinue (category III) oxytocin infusion
 - Reposition the patient
 - Give IV fluid bolus as ordered by the obstetric provider
 - Notify obstetric provider
 - Immediate evaluation for category III by obstetric provider
 - Consider amnioinfusion or tocolytics as ordered by the obstetric provider
- Oxytocin infusion may be restarted according to our current standard of care guidelines below
 - o If oxytocin was off for <30 minutes – restart oxytocin at $\frac{1}{2}$ the rate that cause the uterine tachysystole, then increase as ordered
 - o If off for >30 minutes – restart at the initial protocol dose and increase as ordered
 - o If obstetric provider can change the rate of increase as deemed clinically appropriate
- The study oxytocin infusion will be discontinued at time of delivery (regardless of mode of delivery) with transition to standard postpartum oxytocin dosing protocols as is standard of care.

Commented [SA1]: Make sure these are the protocols we use for each, confirm with [name] on both

Commented [WAM2R1]: I pulled these directly off of the nursing Pitocin protocol

Visit #2

4.4 Additional Baseline Procedures

- Routine intrapartum care will be provided by the patient's managing obstetric team.
- A trained and experienced study team will be responsible for all research data abstraction.
- Maternal outcomes will be assessed following delivery.
- The PI and faculty sponsor will review and validate the diagnosis for all subjects identified to have the primary outcomes. If there is uncertainty, a faculty sponsor will review the chart, discuss with the study team, and make a final determination regarding the outcome.
- Data collection forms will be used during these processes and charts will be reviewed up to 30 days postpartum. We will collect demographic data, as well as data related to the patient's intrapartum course, delivery, immediate postpartum period while inpatient, and neonatal outcomes while inpatient.
- Subject's participation will end following delivery.

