4.5 Study Visits/Follow-Up

No extra postpartum follow-up visits will be performed.

[figure not shown]

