4.9 Secondary Outcomes

- Rate of primary cesarean delivery
- Mode of delivery (including operative vaginal delivery)
- Maximum dose of oxytocin infusion
- Uterine tachysystole without fetal heart rate (FHR) changes

- Uterine tachysystole with FHR changes
- Uterine tachysystole requiring cessation of oxytocin
- Incidence of postpartum hemorrhage
- Incidence of placental abruption
- Maternal side effects (including nausea/vomiting requiring antiemetics, diarrhea)
- Chorioamnionitis ("IAI" or "triple I")
 - o A presumptive diagnosis can be made in women with:
 - Fever $\geq 39.0^{\circ}\text{C}$ (102.2°F) one time or 38.0°C (100.4°F) to 38.9°C (102.02°F) on two occasions 30 minutes apart, without another clear source, PLUS one of the following:
 - Baseline fetal heart rate >160 beats/min for ≥ 10 minutes, excluding accelerations, decelerations, and periods of marked variability
 - Maternal white cell count $>15,000 \text{ mm}^3$ in the absence of corticosteroids and ideally showing a left shift (bandemia)
 - Purulent-appearing fluid coming from the cervical os visualized by speculum examination
 - o A confirmed diagnosis of chorioamnionitis can be made in women with:
 - All the above plus one or more of the following objective laboratory findings:
 - Positive Gram stain of amniotic fluid
 - Low glucose level in amniotic fluid
 - Positive amniotic fluid culture
 - High white cell count in amniotic fluid in the absence of a blood tap
 - Histopathologic evidence of infection or inflammation or both in the placenta, fetal membranes, or umbilical cord vessels (funisitis)
- Endometritis: must meet the following criteria:
 - o Infection occurs within 30 days after the operative procedure AND
 - o Infection presumed to involve the uterus AND
 - o Patient has at least one of the following:
 - Purulent drainage from a drain that is placed through a stab wound into the abdomen or pelvis
 - Organisms isolated from an aseptically obtained culture of fluid or tissue in the organ/space
 - An abscess or other evidence of infection involving the abdomen or pelvis that is found on direct examination, during re-operative, or by histopathologic examination
- Serious maternal morbidity or death (e.g., uterine rupture, admission to intensive care unit, septicemia)
- Neonatal infection, defined as culture proven sepsis, fever, or a suspicious clinical course that warranted treatment with antibiotics
- 5-minute APGAR score <7

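### Section 4.4 contradicts itself on the postpartum window: charts are reviewed to day 30, but the data to be collected are limited to the inpatient stay, while endometritis is counted to 30 days

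*Combined protocol and SAP*

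**What the plan says.** Five places in the combined protocol and SAP bear on how long mother and newborn are observed.

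- **Section 4.4, chart review:** "Data collection forms will be used during these processes and charts will be reviewed up to 30 days postpartum".
- **Section 4.4, next sentence, on what is collected:** besides demographics, "data related to the patient's intrapartum course, delivery, immediate postpartum period while inpatient, and neonatal outcomes while inpatient". The same section says "Maternal outcomes will be assessed following delivery", with no end date, and "Subject's participation will end following delivery". Section 3 agrees: "The total participation time in the study will be considered terminated following delivery".
- **Section 4.5:** "No extra postpartum follow-up visits will be performed".
- **Section 4.7:** collection covers what is required for the primary and secondary outcomes, from the charts of both mother and newborn. It refers to a data collection sheet submitted to the IRB, which is not among the documents.
- **Section 4.9:** the first endometritis criterion is "Infection occurs within 30 days after the operative procedure AND". Serious maternal morbidity (septicemia is one example) and neonatal infection are also secondary outcomes, with no time window.

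**The concern.** Two abstractors could each follow section 4.4 faithfully and code the same case differently. Take a woman readmitted with endometritis on day 8. One abstractor records it, because her chart is open to day 30 and the outcome definition counts it. The other leaves it out, because it did not arise in the immediate postpartum inpatient period. A newborn treated for infection after going home falls outside the stated scope altogether.

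Two things are at stake. First, late infections would be undercounted in a trial whose stated goal (sections 1 and 11) includes the lowest maternal and neonatal adverse outcomes. Second, under the inpatient reading the window closes at discharge, which comes after randomization and may depend on how labor ended. Route of delivery is itself a secondary outcome, so the length of observation need not be the same in the two arms.

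**Working it through.** **No figure in the plan to reproduce on this point.** The documents give no length of stay, discharge rule, endometritis rate or neonatal infection rate. The sample size (170, or 85 per group, section 13) reproduces: a two-sided t-test with difference 858.6 − 644 = 214.6, SD 494.9, alpha 0.05 and power 0.80 needs 84.46 per group, rounded up to 85. This point does not change it. I use only the 85 per group below.

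**Step 1. The texts side by side.**

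| Source | Latest event recorded |
|---|---|
| Section 4.4, chart review sentence | Day 30 postpartum |
| Section 4.4, data sentence | Discharge, for mother and newborn |
| Section 4.7 | Whatever the secondary outcomes need |
| Section 4.9, endometritis | 30 days, counted from an operative procedure |
| Section 4.9, septicemia and neonatal infection | Not stated |

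The second row cannot be met together with the fourth for a woman who goes home before day 30. The chart review sentence does not settle the matter, because a reader could take 30 days as an outer limit for long admissions.

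**Step 2. The start of the endometritis window.** It runs from an operative procedure. A vaginal birth without one has no stated start, so the definition does not clearly apply to it.

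**Step 3. What the inpatient reading could do to the comparison.** This is illustration only; every input except 85 is assumed. Let the true 30-day risk *r* be the same in both arms and for both routes, at 2% to 5%. Let *c* be an arm's cesarean share, and *k*C and *k*V the fractions of events that appear before discharge after cesarean and vaginal birth.

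Observed risk = *r* × [*c* × *k*C + (1 − *c*) × *k*V]

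- Equal shares (25% in both arms), capture 60% and 40%: 0.25 × 0.60 + 0.75 × 0.40 = 0.45 in each arm. Ratio 1.00, but 55% of events are lost in both.
- Shares 30% (low dose) and 20% (high dose), capture 60% and 40%: low 0.18 + 0.28 = 0.46; high 0.12 + 0.32 = 0.44. Ratio 0.44 / 0.46 = 0.96.
- Shares 35% and 15%, capture 70% and 30%: low 0.245 + 0.195 = 0.44; high 0.105 + 0.255 = 0.36. Ratio 0.36 / 0.44 = 0.82.
- Full capture to day 30: ratio 1.00 whatever the shares.

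**Step 4. Event counts.** In the two unequal-share cases, expected recorded events per arm run from 85 × 0.02 × 0.36 = 0.6 to 85 × 0.05 × 0.46 = 2.0. With full capture they run from 85 × 0.02 = 1.7 to 85 × 0.05 = 4.25.

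**The case against.** The strongest reply is that the plan already intends follow-up to day 30. The chart review sentence comes just before the inpatient one, its length matches the endometritis window, and section 4.7 commits to collecting what the outcomes need. The unseen data collection sheet may list late infections. Participation ending at delivery is no obstacle either: there are no extra visits and section 7 draws all material from charts, so abstraction can continue afterwards. All of this stands. A reader might infer that collection definitely stops at discharge; the documents do not support that. They support only that the text says both things.

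A reader might also infer that the infection comparison is biased by route of delivery. That is not shown. It needs a difference between arms in route or postpartum stay, and also a failure to record events after discharge. The documents establish neither. Section 2 cites one trial with fewer primary cesareans on high dose and another with no significant change. Section 11 expects a shorter total admission with shorter labor, which is not the same as a shorter postpartum stay. With the few events expected, a ratio of 0.96 or even 0.82 would be lost in chance variation.

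For newborns, the inpatient limit is the only one stated and no neonatal outcome carries a 30-day window. Extending their window is therefore a recommendation for consistency, not the repair of a contradiction.

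The reply does not remove the conflict between the two consecutive sentences in section 4.4, or between the second of them and the endometritis definition.

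**Conclusion.** The point holds as an internal contradiction about postpartum ascertainment. If abstractors follow the inpatient wording, they will miss endometritis and septicemia after discharge, and newborn infection after discharge will be out of scope. Observation time will then depend on discharge date.

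The size cannot be computed from the documents. Under the assumed inputs, the distortion of the risk ratio ranges from none (equal cesarean shares) to 0.82 (a deliberately wide contrast). The more certain loss is of events: about 0.6 to 2.0 recorded per arm in the unequal-share cases, against 1.7 to 4.25 if all were captured. Those counts rest on the assumed 2% to 5% risk and the assumed capture fractions.

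Only secondary postpartum and neonatal outcomes are touched. The primary outcome (sections 4.8 and 13) and outcomes fixed at or near birth are not. It should be corrected because it decides which safety events are counted and costs almost nothing to settle.

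**What to change.** - **Section 4.4:** replace the two inpatient limits with one fixed window. For example: outcome data will be abstracted from delivery to day 30 for every randomized woman and, in the available record, her newborn, whatever the route of delivery or date of discharge, including readmissions and outpatient encounters.
- **Section 4.9:** count the 30-day endometritis window from delivery, so that it applies to vaginal births as well as cesareans. Give septicemia and neonatal infection the same window.
- **Sections 3 and 4.4:** state that study treatment ends at delivery while chart abstraction continues to day 30. Check that the consent form and the data collection sheet, neither of which is available here, say the same.
- **Section 4.5:** leave as it is; no extra visits are needed.

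The cost is an amendment to the wording and slightly more abstraction within a chart review already planned to day 30. Events treated outside the available records will still be missed, and the report should say so.
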